Forty eight heavy alcohol users between 21 and 70 years old will be recruited through the resources of the Trauma Registry and the Piedmont Triad area. Participants will be prescreened by phone for eligibility. Potentially eligible participants will be invited for an in-person screening visit where, after signing informed consent they will receive a detailed evaluation and urine toxicology screen for illicit drugs. Individuals that remain eligible will then undergo the Stimulation/Scanning (see below).

Inclusion Criteria

1. Ages 21-70.
2. Alcohol use disorder identification test (AUDIT) score >7 or a clinician-determined risk score of Moderate to Severe on the Screening, Brief Intervention, and Referral to Treatment (SBIRT).
3. Drink at least 15 standard sized alcohol beverage servings per week sometime in the past month or have had a blood alcohol level of 140+ on admission to the trauma unit following injury.

Exclusion Criteria

1. Current use of prescription or illicit psychoactive drugs (except marijuana or nicotine) known to decrease seizure threshold by self-report in the last 30 days.
2. Currently meets DSM-V criteria for substance use disorder for a substance other than alcohol, marijuana, or nicotine.
3. Has current suicidal or homicidal ideation.
4. Not currently in or at risk for withdrawal, as indicated by CIWA-Ar >5.
5. History of seizures and/or seizure disorder(s).
6. Females of childbearing potential who are pregnant (by urine HCG), planning to become pregnant, nursing, or who are not using a reliable form of birth control.
7. Any other violation of MRI/TMS safety measures.
8. Unable to read and understand questionnaires, assessments, and the informed consent.
9. No presence of metal objects in the head/neck.
10. History of traumatic brain injury resulting in hospitalization, loss of consciousness for more than 10 minutes, and/or having ever been informed he/she has an epidural, subdural, or subarachnoid hemorrhage.

Sample Size

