Visit 1. Informed Consent and Screening Assessments: All informed consent and Privacy procedures are done in accordance with Good Clinical Practice Guidelines and all study procedures will be approved by the Wake Forest Institutional Review Board before they are executed. Study personnel will review the consent and HIPAA documents with the participant and obtain a signature. Following this procedure

several assessments related to drug use history, past medical history will be administered at Visit 1. Several rating scales assessing alcohol use severity, craving, and past month drinking history will be administered at the screening visit and updated at each subsequent visit.

As typically done in cue-induced craving studies for both Visit 1 and Visit 2, study personnel will ensure that craving levels are at or below baseline before the participant finishes the visit.

Visit 2: Stimulation/Scanning Visit T1 MPRAGE: Participants will be scanned using a Siemens 3.0T Skyra (Siemens Medical, Erlangen, Germany) MRI scanner with a 32-channel head coil. High-resolution T1-weighted structural images will be acquired using a magnetization prepared gradient echo (MPRAGE) sequence [TR/TE=1900ms/2.34ms; FOV=220mm; matrix=256x256 voxels; 192 slices; slice thickness=1.0mm with no gap; final resolution=1mm³ voxels]. This sequence will be acquired before and after TBS in order to maximize coregistration at each scanning session.

Alcohol Cue-reactivity task: The alcohol cue reactivity task which has been used by our group in the past (Schacht et al 2013, Kearney-Ramos et al 2018) will be administered in the MRI scanner as a block design using E-Prime software (Psychology Software Tools, Inc.). The total task time was 12 mins and consisted of six 120second epochs. Each epoch includes alternating 24-second blocks of four task conditions: Alcohol Cue, Neutral Beverage Cue, Blur, and Rest. Respectively, these task conditions included images of alcohol-related stimuli customized for each group (e.g. liquor bottle); neutral stimuli (e.g. water bottle); blurred stimuli acting as visual controls matched by color and hue; and a fixation cross for alert rest periods. T2* multiband EPI Acquisition. Functional images will be acquired with a multislice multiband gradient-echo planar imaging (EPI) sequence [TR/TE=1200ms/35ms; FOV=192mm; matrix=64x64 voxels; 36 slices; slice thickness=3mm with no gap; final resolution=3mm³ voxels]. Each functional run will consist of 656 time points.

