4. **Potential for reflex syncopal event:** Syncope is defined as a momentary loss of awareness and postural tone. It typically has a rapid onset, short duration, and spontaneous recovery. Although syncopal episodes are very rare with TMS (less than 1%), they typically occur during the motor

- threshold procedure before the rTMS treatment has begun. Individuals that are sleep deprived and have low or unstable blood pressure are at greater risk.
5. Interaction with electrical or metal implants: Electrically, magnetically or mechanically activated implants (such as cardiac pacemakers), as well as clips on blood vessels in the brain may be affected by rTMS (as well as MRI) and cause pain or abnormal signal propagation. Although the pain has not reported to be significant protocol-approved research study members will conduct a thorough TMS safety questionnaire. This questionnaire will be checked and updated throughout the course of the study. Individuals that have these implants and devices or suspect that they may have pieces of metal in their eyes, head, or body (e.g. bullets, shrapnel, and fragments from metallurgy) will be excluded from the study in order to minimize any discomfort and abnormal signal propagation.

Risks regarding Randomization and Alcohol Related Cues:

Given that participants will be exposed to alcoholic beverages, there may be an added risk of induced cravings. However, it should be noted that the alcohol cues that participants will be exposed to are not as powerful as the daily cues that participant's encounter in their normal living environment. In addition, participants that will be randomized receive the placebo treatment may prove to be less effective than real study treatment(s) or other available treatments.

Risks regarding Confidentiality:

Despite efforts to maintain subjects' anonymity and confidentiality, there is always some minimal risk of people other than the study investigators gaining access to your health information. Every effort will be made to ensure that your health information will be collected and stored in a manner that ensures the highest level of protection of confidentiality.

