Additionally, a chart review will be conducted for research purposes. Potentially eligible patients will be identified. The potentially eligible patients in the PIs practice will be informed about the study as the PI feels is appropriate. Then potential patients who have agreed to be contacted for future research by logging their WFU Research Permissions preferences in MyChart will be contacted by phone and invited to participate. All other patients will be contacted through their providers to be informed of the study if the provider feels it is appropriate.

Informed consent will be reviewed with the potential participant by a member of the key personnel on this visit. The consent will be signed by the participant as well as one of the Key Personnel on the proposal. A copy of the consent will be given to the subject and the original placed in the research record. The consent and HIPAA process will be done in [name] research laboratory and facility.

Informed Consent

Individuals that have previously consented to be contacted about future research studies will be contacted and phone screened to determine preliminary eligibility. They will be scheduled for their screening visit, which will take place in a private, quiet screening room in the Clinical Neuromodulation Laboratory space in [name] research suite. Informed consent will be reviewed with the potential participant by a member of the key personnel on this proposal. The consent will be signed by the participant as well as one of the Key Personnel on the proposal. A copy of the consent will be given to the subject and the original placed in the research record. All records will be stored in locked departmental files. Section 301(d) of the Public Health Service Act of November 4, 1988 also protects a layer of protection for the privacy of health information for individuals that engage in federally funded medical research.

Confidentiality and Privacy

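### Exclusion 10 counts a brain haemorrhage only if the participant was told of it, names no source for its other two limbs, and is not tied to the chart review already planned

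*Combined protocol and SAP*

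**What the plan says.** All references are to the combined protocol and SAP.

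- **Exclusion Criteria, item 10.** The first two limbs read "History of traumatic brain injury resulting in hospitalization, loss of consciousness for more than 10 minutes". The third reads "and/or having ever been informed he/she has an epidural, subdural, or subarachnoid hemorrhage".
- **Inclusion Criteria, item 3.** One of two alternative ways to qualify is to "have had a blood alcohol level of 140+ on admission to the trauma unit following injury". The other is weekly alcohol intake.
- **Screening steps.** Under Subjects selection criteria, "Participants will be prescreened by phone for eligibility", and an in-person evaluation follows. Under Interventions and Interactions, "several assessments related to drug use history, past medical history will be administered at Visit 1". Under Other potential risks, item 5 (implants and metal), "protocol-approved research study members will conduct a thorough TMS safety questionnaire". The COVID-19 text under Setting allows for screening by video.
- **Subject Recruitment Methods.** Some trauma inpatients are screened and consented during their admission. Then: "Additionally, a chart review will be conducted for research purposes". The use stated for that review is to find people who may be eligible.
- **Structural MRI (Visit 2).** A T1 scan precedes stimulation. Its stated uses are coregistration and coil guidance; no eligibility read is mentioned.

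**The concern.** The haemorrhage limb depends on a conversation having taken place, not on a finding. A bleed on a trauma scan that was never explained to the patient, or was explained while the patient was intoxicated and then forgotten, is a fact in the record that the limb does not reach. The unconsciousness limb is worded as fact, but the person concerned is often the worst witness to it, more so if intoxicated at the time.

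Two things are at stake. The first is safety. The protocol does not say why item 10 exists, but its discussion of seizure risk mentions brain injury as relevant history. The Trial Stopping Rules pause the trial on any serious adverse event and end it if the event is confirmed as directly related to the protocol. The second is precision. Unrecognised brain injury could add variability to cue-evoked connectivity and to Stroop speed and errors, with 24 planned per arm. Because allocation is randomised, the expected effect is noise rather than systematic bias.

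**Working it through.** The plan states no figure on this point, so there is nothing to reproduce. The check is a reading of the text, followed by a short illustration.

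**1. What triggers each limb**

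| Limb | Worded as | Source named |
|---|---|---|
| Brain injury leading to a hospital stay | fact of history | none |
| Unconsciousness beyond 10 minutes | fact of history | none |
| Epidural, subdural or subarachnoid bleed | having been told | the participant, by implication |

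Other exclusions do name their evidence: item 1 self-report, item 4 a CIWA-Ar score, item 6 a urine test.

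**2. Whether any step supplies the missing source.** The phone call, the screening evaluation, the Visit 1 history, the safety questionnaire, the chart review and the T1 scan were each checked. None is said to verify item 10 against trauma records or head imaging. None is said to be barred from doing so.

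**3. Four cases put through the wording**

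- *Admitted because of a head injury with a bleed, never told.* Excluded by the hospitalisation limb, whatever the person recalls, provided someone looks.
- *Admitted for another injury, small bleed found incidentally, never told.* It is arguable whether brain injury led to the stay. The haemorrhage limb would settle it but is not triggered. The person can pass.
- *Bleed with no hospital stay for brain injury, never disclosed.* Neither limb is triggered. The person can pass.
- *Unconscious beyond 10 minutes, cannot recall it, admitted for another injury.* Excluded by the words, but found only if someone looks beyond the interview.

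**4. Size.** The documents give no rate of intracranial findings, no rate of non-disclosure, and no split between trauma and community recruits. The 24 under Sample Size is the size of each arm, not the number of trauma recruits. As an illustration only, let p be the share of enrolled participants with an excluded brain injury that screening missed. The chance of at least one among n is 1 − (1 − p)^n, and the expected number is n × p.

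| Assumed p | At least one of 48 enrolled | At least one of 24 on real iTBS | Expected on real iTBS |
|---|---|---|---|
| 1% | 0.383 | 0.214 | 24 × 0.01 = 0.24 |
| 2% | 0.621 | 0.384 | 24 × 0.02 = 0.48 |
| 5% | 0.915 | 0.708 | 24 × 0.05 = 1.2 |
| 10% | 0.994 | 0.920 | 24 × 0.10 = 2.4 |

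No row is supported by the documents. The table shows only that, in a trial of 48, even a small miss rate gives a sizeable chance of one case.

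**The case against.** The strongest reply is that the first limb already does most of the work. Trauma recruits come from an inpatient unit or its registry, and anyone hospitalised for a traumatic bleed is out regardless of memory or disclosure. This stands, and it limits the point to the residual cases above. A reader might infer that the whole exclusion rests on what people remember or were told, or that anyone with a recorded but undisclosed bleed gets through. The text does not support either: only the haemorrhage limb is conditioned on being told.

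A second reply is that reliance on self-report for the other limbs is an inference. Where the plan means self-report it says so, as in exclusion 1, and the content of the screening evaluation and safety questionnaire is not shown. This also stands. What can be said is that the source is unstated, not that it is recall.

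A third reply is that a chart review meant to find eligible patients may well cover exclusions, and that a blood alcohol value on admission is itself the kind of item read from a record. That is plausible, but the plan does not say it. Even a full chart review would not cure the haemorrhage limb, whose wording still asks whether the person was informed.

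Finally, no link is shown between a missed injury and a serious adverse event, and half of those enrolled receive sham. Both are correct, and both bear on severity.

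**Conclusion.** The point holds in a narrow form. As worded, item 10 can miss a recorded bleed that was incidental, was not the reason for admission or was never disclosed. It can also miss a period of unconsciousness that the person cannot recall, if no one checks beyond the interview. The planned chart review could close both gaps but is not assigned to do so.

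How often this would happen cannot be derived from the documents. A reader might be tempted to put a count on it by treating half of the sample as trauma recruits and applying rates of bleeding and non-reporting. None of those inputs is in the plan, so such a count should not be relied on.

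The conclusion rests on the wording of item 10, on intoxication at injury being one accepted entry route (not the only one), and on the absence of any stated record check for this item. It is a cheap improvement of low severity.

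**What to change.** For participants recruited through the trauma unit or registry:

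1. State that all three limbs of exclusion 10 are determined from the medical record as well as self-report, and that this is completed before stimulation.
2. Assign the check to the chart review already planned under Subject Recruitment Methods.
3. Reword the haemorrhage limb so that it applies when a bleed is *documented in the medical record or reported by the participant*.

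Only the source of evidence changes. The 10-minute limit, the types of haemorrhage listed and the other clinical content of item 10 stay as the investigators set them.

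The cost is a short protocol edit, a few minutes of chart time per trauma recruit, and slightly more screen failures.

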Hence, the goal of this proposal is to evaluate **Strategy 2 of the CNDS theory- increasing activity in executive control circuitry- as an innovative approach to dampening alcohol cue-reactivity (Aim 1) and improving cognitive control in the presence of an alcohol cue (Aim 2)**. This will be achieved through a double-blind, sham-controlled cohort study in 48 heavy alcohol drinkers with a history of alcohol-related injury. The brain reactivity to alcohol cues (Incentive Salience) and cognitive performance in the presence of an alcoholic beverage cue (Cognitive Control) will be measured immediately before and after participants receive real or sham intermittent theta burst stimulation (iTBS- a potentiating form of transcranial magnetic stimulation) to the dorsolateral prefrontal cortex (dLPFC iTBS). iTBS is a high-potency form of brain stimulation wherein two minutes of iTBS (600 pulses) leads to an increase in cortical excitability that lasts for approximately 30 minutes (Huang et al. 2005). In 2018, dLPFC iTBS was FDA-cleared as a treatment for major depressive disorder (wherein 30 sessions over 6 weeks lead to a sustained decrease in depressive symptoms for 6 months; Blumberger et al. 2018). In 2019, the first 2 manuscripts were published demonstrating that iTBS decreases cue-reactivity to cocaine (Steele et al 2019, Sanna et al 2019). **The goals of this pilot study are to quantify the acute effect of a single session of real or sham dLPFC iTBS on brain response to alcohol cues (Aim 1) and cognitive flexibility in the presence of an alcohol cue (Aim 2) among risky drinkers (“target engagement”)**.

Aim 1: Evaluate the effect of dLPFC iTBS on alcohol cue-reactivity. The blood-oxygen level dependent (BOLD) signal associated with exposure to alcohol cues will be measured before and after sham and real iTBS using a validated, patient-tailored alcohol/non-alcoholic beverage cue task. Hypothesis: cue-evoked functional connectivity in the dLPFC, ACC, amygdala, and ventral striatum will be attenuated after real but not sham iTBS.

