Aim 2: Evaluate the effect of dLPFC iTBS on cognitive performance in the presence of an alcohol cue. Following the alcohol cue reactivity task all individuals will perform the well-known alcohol Stroop task (downloaded from the NIH toolbox) on a Tablet PC while a glass of the participant’s preferred alcoholic beverage (beer, wine, liquor) is placed within 5 feet of the participant (but out of arms length). This will occur before and after TBS. The participant will not be allowed to consume the drink. Hypothesis: Stroop accuracy and reaction time will be impaired at baseline, but this difference will be attenuated by real (but not sham) iTBS to the dLPFC (three way mixed model ANOVA, correcting for multiple comparisons).

Methods and Measures

Design

Our primary goal is to determine the extent to which one session of dLPFC iTBS can attenuate limbic circuitry involved in alcohol cue-reactivity (Aim 1) and cognitive control in the presence of an alcohol cue (Aim 2) among heavy alcohol users with a history of risky drinking behavior. This will be tested in a cohort of 48 heavy alcohol users, recruited through the resources of the Wake Forest Trauma Unit Registry and from the community at large through advertisements. This double-blind, sham-controlled study will involve 1 Screening visit and 1 TBS/MRI Scanning Visits. At the scanning/stimulation visit, functional MRI data will be collected before and after exposure to a session of real or sham theta burst stimulation (Figure 1). TBS will be applied over the left dorsolateral prefrontal cortex (landmark based on EEG 10-20 system: F3). A series of clinical assessments of drinking behavior and other relevant psychosocial and demographic measurements will also be collected (Table 1). We will test the hypotheses that TBS over the dLPFC will attenuate the neural response to alcohol cues (Aim 1) and improve cognitive performance in the presence of an alcoholic beverage cue (Aim 2). The results of these aims will be further evaluated in terms of their relationship to alcohol drinking severity and demographic factors. These data will be preliminary data for a subsequent R01 focused on the sustained effects

of multiple sessions of TBS as a tool to decrease drinking among individuals with AUD and lowering morbidity and hospital recidivism among these patients.

Setting

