To determine the minimum number of participants necessary we performed a power calculation for the experiment based on our prior (Kearney-Ramos et al 2018). Based on the mean and standard deviation of mPFC activity in that study, Aim 1 will require 22 participants in both the real iTBS group and the sham iTBS group (95% power using two sided $p < 0.05$ level of significance). Assuming some loss of functional MRI data to movement artifacts (10%) we are proposing to enroll 48 participants (24 per group (real vs sham; 16 women (33%), 32 men (66%) based on prevalence of AUD in the US population. Integrity of the sham-control. The integrity of the blind will be assessed at the end of each visit with a standardized questionnaire regularly used in clinical trials of rTMS treatments. The randomization scheme for the study will be developed and monitored by a biostatistician associated with the Comprehensive Cancer Center's Biostatistical Shared Resource (to be named), and will be given to a member of the study team that has no contact with the participant. This person will set the MagVenture sham-controlled TMS system up before the PI, Co-I or research assistant enter the room with the patient. The data will be analyzed by the PI, Co-I and research assistant who will remain blinded until the end of the study.

Based on recruitment history from similar intervention studies in these individuals at Wake Forest Baptist hospital we anticipate that we will be able to recruit 3-4 participants per month (12-16 months = 48 participants). We have planned for 2 months of initial implementation and quality control assessment of the MRI scanning paradigm. Recruitment will commence in month 3 and likely continue through month 19. Data analysis (blinded) for Aim 1 (preprocessing, functional connectivity assessment) and Aim 2 (analysis of quality, rigor, and basic signal detection) will be ongoing. Months 20-24 will be spent performing final analyses, unblinding, preparing data for an R01 application and integrating outcomes with the clinical and preclinical projects within the WF-TARC in order to plan for future translational collaborations.

[figure not shown]
Interventions and Interactions

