Generalized Psychophysiological Interaction (gPPI): gPPI will be used to investigate task-modulated patterns of functional connectivity (FC) during the alcohol cue reactivity task. Regions-of-interest (ROIs) comprising frontal-striatal circuitry as well as elements of the Salience Network and Central Executive Network will be identified from the standard Automated Anatomical Labeling (AAL) Atlas. These included the vmPFC (AAL: left and right Frontal_Med_Orb), left caudate (AAL: Caudate_L), right caudate (AAL: Caudate_R), left putamen (AAL: Putamen_L), right putamen (AAL: Putamen_R), left insula (AAL: Insula_L), right insula (AAL: Insula_R), and anterior cingulate cortex (AAL: left and right Cingulum_Ant). These ROI masks will then be used in CONN Toolbox to extract ROI timecourses from

the fMRI data for subsequent gPPI computation. The Drug/Alcohol vs. Neutral contrast β s from the Pre- and Post-Real cTBS and Pre- and Post-Sham cTBS were entered into a two-way ANOVA and subsequent *t*-tests to determine the effect of treatment on changes in drug cue-evoked FC. More details on the analysis can be found in prior publications from our group (Kearney-Ramos et al 2018).

Results will be analyzed initially using descriptive statistics. Comparison between groups will be done using chi square tests for proportions, and *t*-tests or ANOVA procedures for continuous variables. Regression analysis will be performed to identify independent outcome predictors. Other inferential statistical analysis will be conducted as appropriate.

Relationship with the WF-TARC Goals:

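### Aim 1 is powered on mPFC activity but analysed as functional connectivity, with no primary connection named and an ROI list that omits the stimulated region

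*Combined protocol and SAP*

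**What the plan says.** **Sizing.** Under Sample Size: "Based on the mean and standard deviation of mPFC activity in that study, Aim 1 will require 22 participants" in each group, at 95% power and two-sided 0.05. With 10% loss of fMRI data to movement, enrolment is 48 (24 per group). No mean, SD, effect size or test is given.

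**Measure.** Objectives introduces Aim 1 as a BOLD measure: the "signal associated with exposure to alcohol cues will be measured before and after sham and real iTBS". Design likewise expects that "TBS over the dLPFC will attenuate the neural response to alcohol cues (Aim 1"). But the hypothesis stated under Aim 1 is that "cue-evoked functional connectivity in the dLPFC, ACC, amygdala, and ventral striatum will be attenuated after real but not sham iTBS". The timetable in Sample Size describes the work as "Data analysis (blinded) for Aim 1 (preprocessing, functional connectivity assessment"). In Outcome Measure(s)/Analytical Plan the single imaging outcome analysis is gPPI: "gPPI will be used to investigate task-modulated patterns of functional connectivity (FC) during the alcohol cue reactivity task".

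**Regions.** That section says that frontal-striatal regions and "elements of the Salience Network and Central Executive Network will be identified from the standard Automated Anatomical Labeling (AAL) Atlas". It then lists eight ROIs: vmPFC, left and right caudate, left and right putamen, left and right insula, and ACC.

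**Test.** Pre and post values for real and sham enter a two-way ANOVA followed by t-tests, "to determine the effect of treatment on changes in drug cue-evoked FC". The stimulation named there is cTBS, although this trial gives iTBS. Further detail is left to the group's earlier publications. The document's only mention of correction for multiple comparisons, and its only primary dependent measures, belong to the Aim 2 Stroop task.

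**The concern.** A sample size supports a power claim only for the measure, contrast and test that it was computed for. Here the inputs are a mean and SD of regional activity, and the planned outcome is a task-modulated connectivity contrast. The two have different scales, variances and plausible effects, so one does not give power for the other.

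Two further gaps make this matter. The ROI list does not let the stated hypothesis be tested in full, and the region missing most conspicuously is the one being stimulated. With many possible connections and none designated, the 5% error rate quoted in the sizing also has no defined test to attach to. Design says that these results will be preliminary data for an R01. A connection picked after the fact, presented as coming from a study with 95% power at 5% error, could carry a chance finding into that application.

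**Working it through.** **1. Can the 22 be reproduced?** No, because no effect, SD or test is stated. Solving backwards from 22 per group, 95% power and two-sided 0.05:

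- Two groups, normal approximation: d = (1.960 + 1.645) × √(2/22) = 1.087.
- Two groups, noncentral t (df 42, noncentrality d√(22/2)): d = 1.113.
- Within-group paired t with n=22: standardised change 0.807.

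The implied effect therefore depends on a test that the plan does not name. The arithmetic to 48 is not at issue: 24 × 0.9 = 21.6 evaluable per group, just under 22.

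**2. Where do the inputs come from?** Application to AUD and Objectives cite two 2018 papers side by side in different short forms. Sample Size uses the form that matches reference 16, whose title describes vmPFC stimulation and cue reactivity. So the inputs come from a different stimulation target as well as a different measure.

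**3. Hypothesised regions against listed ROIs.**

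| Region in Aim 1 hypothesis | In the gPPI ROI list? |
|---|---|
| dLPFC (stimulation target) | No |
| ACC | Yes |
| Amygdala | No |
| Ventral striatum | No mask so labelled; whole caudate and putamen are listed |

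Two of four are missing if caudate and putamen are taken to cover ventral striatum, and three of four by name. The dLPFC gap also conflicts with the section's own description, because Relationship with the WF-TARC Goals calls the dLPFC a node of the Central Executive Network. The vmPFC is in the list, so the sizing mismatch is one of measure (activity against connectivity), not of an absent region. The mPFC does not, however, appear in the Aim 1 hypothesis.

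**4. Error rate with no primary (illustration).** The plan does not state the number of tests. Eight ROIs give 8 × 7 / 2 = 28 pairs. If all are tested at 0.05 under the null:

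- independent: 1 − 0.95^28 = 0.762;
- equicorrelated normal statistics, correlation 0.5: 0.491;
- equicorrelated normal statistics, correlation 0.9: 0.169.

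**5. What the planned N can detect.** Take 21.6 evaluable per arm, one two-sample t-test on pre-to-post change at two-sided 0.05 (assumed), df = 2 × 21.6 − 2 = 41.2 and noncentrality d√(21.6/2):

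| Power | Detectable d |
|---|---|
| 80% | 0.87 |
| 90% | 1.01 |
| 95% | 1.12 |

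**The case against.** **It is a pilot of target engagement, so formal error control is optional.** A single primary with Holm or FDR is not the only acceptable design. But the protocol itself claims 95% power at two-sided 0.05, and that claim needs a defined measure.

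**The details may be in the earlier publications.** They may, and so may the mean and SD. It can be said only that they are not in this document. A general pointer to past work, in a paragraph that names cTBS, does not designate this trial's primary connection.

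**The ROI list may not be exhaustive.** It is introduced as what the ROIs included, so other masks could exist. If so, they should be written down. As it stands, the stimulated region is not there.

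**The group comparison is already planned.** Largely so: the two-way ANOVA uses pre and post values under real and sham. The plan does not say which effect, on which connection, carries the Aim 1 conclusion.

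Some stronger readings are tempting but not supported:

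- *Any correction would cut power below 95%.* Bonferroni over 28 pairs would: at d=1.113 and 22 per group, power falls to about 64%. Fixed-sequence testing keeps the full alpha for the first connection.
- *The 50% analysis inflates the error to about 8.3%.* That figure requires a group test at 0.05 at both the half-way and final analyses. Data and Safety Monitoring places the half-way analysis under an efficacy heading but describes no efficacy claim or stopping rule, and Sample Size keeps the analysts blinded until the end of the study.

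**Conclusion.** The concern holds, and should be fixed before any analysis by group. The 95% power claim is not supported for the connectivity analysis that the plan specifies. At least two of the four hypothesised regions, including the stimulated one, cannot be tested with the ROIs listed. Aim 1 has no named primary connection and no stated multiplicity control.

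A reader might infer that 22 per group is wrong or that the trial is underpowered. The documents do not show that: the figure is unverifiable, and a connectivity effect of d=1.12 or more would still have about 95% power on one pre-named test. Nor do they establish that most hypothesised regions are missing, since it is half if whole caudate and putamen count as ventral striatum.

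The range of 17% to 76% for family-wise error is an illustration. It assumes that all 28 pairs are tested uncorrected, with correlation from 0.9 down to independence. The detectable differences assume a two-sample t-test on change and 10% data loss in each arm.

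**What to change.** Keep N=48. Before any analysis by group:

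1. Add dLPFC and amygdala masks to the gPPI list, and either add a ventral striatum mask or state that caudate and putamen serve as it, so that the list agrees with the Aim 1 hypothesis. Correct the reference to cTBS.
2. Name one primary connectivity measure among the hypothesised regions. Test it as the group-by-time interaction (real versus sham difference in pre-to-post change) at two-sided 0.05. Report all other connections as secondary under Holm or FDR control.
3. Replace the 95% power statement with the detectable standardised differences in the last table under working.
4. State that the 50% analysis will not be used to claim efficacy on that measure, in keeping with blinding to the end of the study.

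If the sponsor prefers mPFC activation as primary, that region and measure must be added to the Aim 1 hypothesis and the activation contrast specified. The mean, SD and test behind 22 must then be stated, or the power restated as in item 3.

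The cost is up to three added masks, or one added contrast, and a less favourable power statement. No extra participants or scans are needed.
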